In this split-mouth study, the patients will receive the control, 3-0 vicryl rapide suture, on one side and the intervention ,3-0 V-loc suture, on the contralateral side.

The allocation of suture material to closure site, left or right third molar surgical site, will be drawn at random prior to the procedure. Allocation will be concealed through pre-sealed envelopes containing the side allocated the intervention. There will be an equal number of sealed allocations, of the intervention, to each site. The site receiving the intervention and the site receiving the control—left or right mandibular third molar—will be recorded in the patient's file. This will aid in ensuring a balanced number of interventions on each side.

Patients will be blinded as to which site receives the control (3-0 vicryl rapide) and which site receives the intervention (3-0 V-loc). However, as part of the consent process, patients will be made aware that both materials will be used.

Study procedure

Surgical procedure

The surgical removal of bilateral similarly impacted wisdom teeth will be performed by the primary investigator ([name]). All procedures will be supervised by a specialist oral and maxillofacial surgeon employed by the University of Otago, or, a senior dental officer at Southland Hospital. We aim to eliminate inter-operator variability and consequent performance bias by involving only a single operator. The surgical removal of the patient's third molars will be carried out at a separate appointment from the initial consultation. This allows the patient to have time to consider their participation in the study and whether they would like to defer of withdraw from the procedure.

Intravenous cannulation will commence following patient identification, confirmation of procedural consent and a 60 second pre-procedural 0.2% chlorhexidine gluconate mouthwash. The procedures will be carried out under intravenous (IV) sedation using midazolam which will be titrated to achieve the desired depth of sedation. Patients will have their height and weight (body mass) taken on the day. There will be a standardised pre-operative dose of 1.2g Amoxicillin/Clavulanic Acid, 8mg dexamethasone and 40mg parecoxib given to all participants. Patients that are allergic to penicillin antibiotics will be given a 1g dose of IV cefazolin; patients that are allergic to beta-lactam antibiotics will receive a 600mg IV infusion of clindamycin over 20 minutes.

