Local anaesthetic (lignocaine 2% with adrenaline 1:100 000) will be administered via an inferior dental block and buccal infiltration to the procedural sites prior to incision.

A two-sided flap design will be used, where the:

- 1. papilla distal to the first molar will be incised but not relieved,
- 2. the papilla distal to the second molar will be incised and relieved,
- 3. with a distal relieving incision across the external oblique ridge
 - a. In the event further exposure is required, an additional mesial relieving incision incorporating the distal papilla of the second molar will be made, making the flap 3-sided.

b. This will be determined pre-operatively, and where deviation from the planned flap design has occurred, this will be recorded.

The impacted third molar will be removed following any required sectioning of the tooth and bone removal.

The procedural site will be closed with simple interrupted 3-0 vicryl rapide sutures on the control side and the intervention side will be closed with a continuous running 3-0 v-loc suture. The difference in closure pattern is due to the differences in material handling and application.

A prescription for post-operative pain relief including 1g paracetamol, 400mg ibuprofen orally 4 times daily as needed, will be provided. Additional rescue analgesia will be prescribed, consisting of either 30mg codeine phosphate or 50mg of tramadol orally 4 times a day as needed. If required, the rescue analgesia will be recorded as part of the patient's post-operative pain diary. Patients who are unable to tolerate these medications will be excluded from this study.

Patients who require additional monitoring will be reviewed as per the institution's policy around post-operative complications.

Post-operative diary

The participants will be asked to rate the pain intensity as well as irritation from the sutures for the first 48 hours, every 6 hours while awake. A non-graduated visual analogue scale (VAS) will be provided to the patients for recording of this information as part of their pain diary.

The VAS will comprise of two 100mm horizontal lines with no markings along its length. The left end will be anchored with a vertical line and labelled 'no pain' and the right similarly anchored with a vertical line and labelled 'worst pain imaginable'. The score is determined by the distance between the end of the line on the left and the participant's mark.

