- 1. Eligible patients will be invited to participate and will be provided with a copy of the participant information sheet if they express interest. The initial appointment will involve a consultation with the clinician/primary investigator. If the patient provides informed consent to participate, they will then complete the pre-operative questionnaire. This questionnaire contains the Oral Health Impact Profile, OHIP-14 (Slade, 1997), Locker's Global Oral Health Item (Thomson et al., 2012), and the Dental Anxiety Scale (Corah, 1969).
- 2. Patients will be assigned a study participant number which will be used during data collection. This will be recorded separately from their clinical records. According to the applicable institutional protocol, the intervention site, material and batch number will be recorded in the patient's clinical record.
- 3. The type of third molar impaction according to the Winter's classification (mesio-angular, disto-angular, vertical, horizontal, transverse bucco-lingual, inverted) will be recorded for each participant. Clinically and radiographically similar impaction patterns are crucial in a split-mouth design.
- 4. Prior to the procedure, the patient will:
 - i. Complete a VAS score on pre-operative pain and irritation;
 - ii. Have a triplicate of baseline measurements to later aid in assessing facial swelling will be recorded.
 - iii. Have their height and weight taken.

The removal of the bilateral similarly impacted third molars will then commence under IV sedation.

5. The time taken for removal of the mandibular third molar from each side will be recorded, starting from the time of the initial incision to the completion of tooth removal. Both sites will be irrigated and inspected to remove and fine debris in the surgical site, ensure no remnants remain and there is no inadvertent damage to adjacent structures. The time taken for wound closure will also be recorded, starting from the time of the first bite of the soft tissue, to the time the sutures have been placed and the wound edges satisfactorily approximated.

- i. Prior to the procedure, the side receiving the intervention will be drawn.
- ii. This will be drawn at random, with the nurse and the clinician unaware of which side the intervention is assigned to until the envelope is opened.

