Sample size. Power analysis yielded a sample size of 63 participants based on a paired sample t-test analysis with alpha of 0.01, power of 0.9, and a moderate effect size (Cohen's d = 0.5). Previous research supports that moderate to large effect sizes can be expected for our key outcome, closure time (Durand, 2017; Zhu et al., 2017). Furthermore, a simulation study on the sample considerations of split mouth designs also indicated that a sample size of approximately 60 participants would be appropriate. 70 participants will be recruited to account for possible drop-out and data loss from participant protocol deviation.

Statistical approach. Statistical analyses will be conducted using the statistical programming language R. Our outcome variables, closure time, inflammation, and pain, will be modelled using separate mixed models Analyses of Variance (ANOVA) with suture type as a within-subjects variable and age, sex, ethnicity, smoking status, previous pericoronitis and dental anxiety score as between-subjects variables. In the case of inflammation, irritation and pain, we will use a repeated measures design to account for multiple follow-ups. A post-hoc polynomial comparison of follow-up outcomes by suture type will also be used to determine whether the trajectory of healing differed significantly between suture types. In all cases, we will use an alpha

of 0.01, more stringent than the traditional 0.05. Using a lower alpha allows us to be more certain of our findings and also implicitly controls for the multiple comparisons we are making across different outcome variables.

Bias and confounding

Bias

The patient is blinded to which side receives the intervention to minimise reporting bias. Handedness will be controlled for by allocating an equal number of interventions to each of the left and right sides through the randomly selected system of sealed envelopes drawn prior to the procedure. Uneven loss to follow-up or withdrawal may cause one intervention-control-side combination to be over-represented.

Modifiers

Age

Increasing age has been associated with increased procedural difficulty. We have excluded individuals 45 years or older to minimise the effect of age.

Peri-operative medications

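### The protocol never fixes when the side envelope is opened, so the single unblinded operator may know the suture side during the surgery that comes before closure

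*Protocol*

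**What the plan says.** Three places in the Protocol time the draw, and all put it before surgery. Under Randomisation, the allocation of suture to side "will be drawn at random prior to the procedure". Data collection, item 5.i, reads "Prior to the procedure, the side receiving the intervention will be drawn". The Bias section refers to a "randomly selected system of sealed envelopes drawn prior to the procedure".

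Disclosure is described separately. Randomisation states "Allocation will be concealed through pre-sealed envelopes containing the side allocated the intervention". Item 5.ii says the draw is random, "with the nurse and the clinician unaware of which side the intervention is assigned to until the envelope is opened". No section says when the opening takes place.

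On conduct, the primary investigator performs every operation under supervision (Surgical procedure). Blinding is described for patients only (Randomisation; Bias). The standard flap is two-sided, but "In the event further exposure is required, an additional mesial relieving incision" makes it three-sided. The next sub-item (3b) says the flap is settled pre-operatively and that departures from the plan are recorded. Tooth sectioning and bone removal are done as needed. Both sides are operated on in one session (Study design), and their order is not specified. Item 5 has tooth-removal time recorded for each side and starts the closure clock at the first bite of soft tissue.

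**The concern.** The randomised comparison concerns only how the wound is closed. Everything from incision to irrigation should therefore be done in ignorance of which side will get which suture. The text does not secure this. An envelope drawn before the procedure may be opened at once, and one person then makes all the surgical choices on both sides, under a protocol that hypothesises an advantage for knotless closure.

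Those choices could plausibly affect the outcomes listed as primary. A longer incision leaves more wound to close, and closure time is named as the key outcome; tissue trauma may affect pain and swelling. This link is clinical reasoning; the protocol gives no figure for it. The split-mouth design removes differences between patients. It does not remove unequal surgery on the two sides of one patient, and if such inequality followed the allocation it would enter the estimated suture effect.

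**Working it through.** **1. Order of events, and what the text fixes**

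| Step | Where described | Is the side hidden from the operator? |
|---|---|---|
| Draw | Randomisation; Data collection 5.i; Bias | Yes, while the envelope is sealed |
| Opening of envelope | Data collection 5.ii | Time not stated |
| Flap plan | Surgical procedure, 3b | Pre-operative, but not tied to a time before opening |
| Choice of first side | Not described | Not secured |
| Incision and any extension | Surgical procedure, 1 to 3a | Not secured |
| Sectioning and bone removal | Surgical procedure | Not secured |
| Irrigation and inspection of both sites | Data collection 5 | Not secured |
| Closure | Surgical procedure; Data collection 5 | Cannot be hidden |

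The text is compatible with opening at any point from the draw to the first bite. Every row between those two points is exposed if opening is early.

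**2. What could detect a difference afterwards**

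Flap deviations and per-side removal times are recorded, so they can be compared by suture side. Neither appears in the Data entry list. The extent of bone removal and the order of sides are not stated to be recorded. Every covariate named under Statistical approach (age, sex, ethnicity, smoking, previous pericoronitis, dental anxiety) is between-subject, so none addresses a side-to-side difference in surgery.

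**3. The protocol's own sample size**

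Inputs (Sample size): paired t-test, alpha 0.01, power 0.9, d = 0.5, stated n = 63, recruitment 70. Sidedness is not stated.

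Formula: power = P(|T| > t(1 − α/2; n − 1)), where T is noncentral t with n − 1 degrees of freedom and noncentrality d√n.

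- Two-sided: n = 63, noncentrality 0.5 × √63 = 3.97, power 0.901. This reproduces the stated figure.
- One-sided: n = 55. Two-sided normal approximation: 59.5, so 60. Neither matches 63.
- With all 70 analysed, power is 0.934; the allowance for loss is 1 − 63/70 = 10%.

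The sample size is sound and does not depend on when the envelope is opened.

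**4. Illustration on assumed bias**

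Suppose there is no true suture effect but knowledge of the side shifts the mean paired difference by b standard deviations. Putting b in place of d in the same formula gives the chance of p < 0.01:

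| Assumed b | Noncentrality at n = 63 (b√63) | n = 63 | n = 70 |
|---|---|---|---|
| 0 | 0 | 0.010 | 0.010 |
| 0.1 | 0.79 | 0.036 | 0.040 |
| 0.2 | 1.59 | 0.151 | 0.173 |
| 0.3 | 2.38 | 0.398 | 0.450 |

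The values of b are not taken from the protocol, and nothing in it allows them to be estimated.

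**The case against.** The strongest reply is that drawing is not opening. Item 5.ii treats the opening as a distinct event, and no sentence places it before incision. A reader might infer that the operator does know the side throughout the surgery; the documents do not support that. This stands, and it limits the point to an unspecified opening time that permits early knowledge. It does not remove the point, because the draw is timed in three places and the opening in none.

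Safeguards also exist: bilaterally similar impactions are required, every procedure is supervised, the flap is planned pre-operatively with deviations recorded, and removal is timed on each side. A reader might infer that unequal surgery could never be told apart from a suture effect. That goes too far, since flap deviations and removal times can be compared by suture side. The check remains partial: flap planning may follow opening, and bone removal and side order are not covered.

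A reader might also take the protocol to claim that one operator abolishes all performance bias, from the words "performance bias by involving only a single operator". In full, the sentence concerns bias consequent on differences between operators, which a single operator does remove. It is not an error.

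A warning against adjusting for flap type or removal time would be beside the point, since neither is a listed covariate. Finally, the illustrated error rates would follow from a bias of that size from any source, and the largest assumed shift is 0.3/0.5 = 60% of the design effect. They are not evidence about this trial.

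**Conclusion.** The concern holds in a limited form. The protocol permits, but does not state, that the single unblinded operator knows the side before closure. This is an avoidable route to bias in closure time, pain and swelling. It is a matter of trial conduct, so no later analysis plan could repair it, and the correction is nearly free; for those reasons it should be made. The actual bias cannot be sized from the document and may be nil if the operator already delays opening. The rates of about 3.6%, 15% and 40% rest wholly on assumed shifts of 0.1, 0.2 and 0.3 SD and a two-sided paired t-test at 0.01 with 63 pairs. They show only that small systematic shifts would undo the strict alpha on which the protocol relies.

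**What to change.** In Randomisation and in Data collection, item 5, state that:

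- the envelope stays sealed until both teeth are removed and both sites are irrigated and inspected, the sequence in which item 5 already lists these steps;
- it is opened immediately before the first suture bite, and the opening time is logged;
- the planned flap for each side and the order of sides are recorded before opening.

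If one site has to be closed before the other tooth is removed, log this. The second removal is then done with the side known, and only the choice of order is protected.

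The cost is a few lines of text, one extra logged time, and both suture packs at hand in every case. Sample size and analysis model do not change. One limit remains: the operator necessarily knows the suture while closing, so bias in closure time that arises during closure itself is not removed.

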Conventional wound closure in third molar surgery involves simple interrupted multifilament sutures. The knot takes time to tie, causes irritation, stress concentration, and is an area of focal weakness in the suture. Clinically, multifilament sutures pose an issue due to capillary action, which draws bacteria and saliva along the material, through the mucosa, and accumulates debris and plaque, which increases inflammation. Since monofilament knotless sutures do not have the same capillary action that multifilament sutures do, they eliminate issues associated with this. The use of knotless sutures in other areas of surgery is supported by a strong body of evidence, however, intraoral usage, particularly in third molar surgery has yet to be explored.

Aims of study

To evaluate the benefits of knotless sutures over conventional sutures for wound closure in third molar surgery.

Objectives

Primary objectives

- To determine if there is any difference in wound closure time between conventional and knotless sutures
- To determine if there is any improvement in post-operative outcomes from using knotless sutures in third molar surgery, measured as:
 - Pain (VAS)
 - Swelling (Facial measurements)
 - Tissue irritation (VAS)

Secondary objectives

- To determine if the savings obtained in operating time reduction justifies the increased material cost of knotless sutures.
 - Is there an impact on overall treatment cost provision?
- Patient's impression on healing of the surgical third molar extraction site and post-operative comfort between the two materials.
- To determine if patients perceive an improvement in QoL following third molar surgery.

Implications

Potential benefits

The current body of literature is built upon clinical studies carried out in other areas of surgery. There is no convincing evidence at present to support or refute the use of knotless sutures in third molar surgery, hence, further clinical investigation would help us evaluate the validity of this particular application.

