- 6. Participants will be asked to rate the pain and irritation experience at each side every 6 hours while awake for the first 48 hours. A non-graduated 100mm VAS, in the patient's post-operative diary will be included, for every waking 6 hour interval.
 - i. They will additionally record under the respective pages:
 - i. The time between the end of the procedure (will be written down into the booklet at the conclusion of the procedure) and the first use of rescue medication
 - ii. The amount of rescue analgesia consumed each day
 - iii. Any adverse events experienced post-operatively (e.g. vomiting, nausea, headaches, uncontrolled pain and swelling from the site)
- 7. Participants will be asked to attend a post-operative review with the primary investigator at 48h following their procedure, and again at 7 days.
 - i. A repeat triplicate of facial swelling measurements will be taken at each of these appointments.
 - ii. A post-operative questionnaire will be completed at each appointment. This contains items relating to post-operative pain, irritation at the sites, whether they needed to be reviewed in a community-based practice or at the institution in the intervening period, whether intervention was required, compliance with the prescribed pain relief, requirement for rescue analgesia, OHIP-14, Locker's global oral health measure. Additionally, the patient's perception of which side they felt was healing better will be recorded.

Measurement of facial swelling

Facial swelling will be determined by tape measurements between the tragus and soft tissue pogonion (A), tragus and lateral corner of the mouth (B), lateral corner of the eye and the angle of the mandible (C). Facial measurements will be calculated as: (A

+B+C)/3, and facial swelling (%) will be calculated as: [(postoperative measurement – preoperative measurement] × 100% (Baqain et al., 2012).

- 1. These measurements will be taken prior to commencement on the day of the procedure;
- 2. 48h post-operatively;
- 3. 7 days post-operatively.

Data entry

Data will be entered into a Microsoft Excel spreadsheet, recording the triplicate of facial measurements, the nature of impaction involved, the time taken to close the surgical site, the intervention side/site and scores from the operative questionnaires. The data will be checked for errors prior to de-identification and data analysis.

Statistical considerations and data analysis

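### The facial swelling formula has no divisor, so the outcome labelled a percentage is 100 times a length; this affects the reported size, not the test or the sample size

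*Protocol*

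**What the plan says.** The Protocol lists swelling under Primary objectives, beside closure time, pain and irritation, with the entry "Swelling (Facial measurements" and a closing bracket.

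The only definition is in Data collection, Measurement of facial swelling. It opens with "Facial swelling will be determined by tape measurements between the tragus and soft tissue pogonion (A" and names two further distances, B and C. It then says "Facial measurements will be calculated as: (A" and completes the expression as the sum of the three divided by 3. The outcome follows in the same sentence: "facial swelling (%) will be calculated as: [(postoperative measurement – preoperative measurement] × 100", with a percent sign after the 100 and a reference to a published split-mouth study of flap design.

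No other section gives a second or corrected formula. Neither that section nor the recording forms in Appendices 1 to 3 state a unit for the tape.

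**The concern.** A percentage change needs a reference value in the denominator. Here the baseline is subtracted and then disappears, so the result keeps the dimension of a length while carrying a percent label. The round bracket that opens before the postoperative term never closes, which suggests that part of the expression is missing.

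Two analysts could follow this Protocol in good faith and produce different variables: absolute change times 100, or change relative to baseline. For an outcome under the primary objectives, that choice should be settled before the data are seen. A literal reading would give a mean difference and confidence interval on a scale that depends on the tape, labelled as percentages, and not comparable with swelling reported elsewhere as a true percentage.

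**Working it through.** **Inputs.** From the Protocol: the facial measurement M = (A + B + C)/3; the printed score, 100 × (M_post − M_pre); the sample-size statement. Assumed, because the Protocol gives no face lengths and no unit: baseline means of 110, 120 and 130 mm, and a rise of 6 mm.

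**1. The plan's own figure.** The swelling section states no numerical result to reproduce. The sample size can be checked: "sample size of 63 participants based on a paired sample t-test analysis with alpha of 0.01, power of 0.9, and a moderate effect size". The standardised difference it assumes is 0.5. For a two-sided paired t-test with n = 63, the degrees of freedom are 62 and the noncentrality is 0.5 × √63 = 3.97. The exact power is 0.9007, and 63 is the smallest n that reaches 0.90. The Protocol does not state sidedness; a one-sided test would need 55. The figure therefore reproduces as two-sided.

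**2. The printed formula against relative change.** Relative swelling is 100 × (M_post − M_pre)/M_pre.

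| Baseline | After 6 mm rise | As printed, mm | As printed, cm | Relative swelling |
|---|---|---|---|---|
| 110 mm | 116 mm | (116 − 110) × 100 = 600 | (11.6 − 11.0) × 100 = 60 | 6/110 = 5.45% |
| 120 mm | 126 mm | (126 − 120) × 100 = 600 | (12.6 − 12.0) × 100 = 60 | 6/120 = 5.00% |
| 130 mm | 136 mm | (136 − 130) × 100 = 600 | (13.6 − 13.0) × 100 = 60 | 6/130 = 4.62% |

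The printed score divided by the relative one is M_pre in whatever unit was used: 110 to 130 in millimetres, 11 to 13 in centimetres.

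**3. Equal relative swelling.** A 5% rise is 5.5 mm on 110 mm and 6.5 mm on 130 mm. As printed these score 550 and 650 in millimetres, although relative swelling is the same.

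**4. Effect on the comparison of sutures.** If one unit is used throughout, the printed score is a constant k times the absolute change. The mean and the standard deviation of the side-to-side differences both scale by k, so t = mean/(SD/√n) and d = mean/SD do not move. Dividing by baseline does change each score, but the two sides of one face have similar baselines.

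One simulated data set of 63 pairs illustrates this. All values are assumed: baseline mean 12 cm, between-patient SD 0.8 cm, side-to-side SD 0.15 cm; mean rise 0.5 cm, with SD 0.3 cm between patients and 0.2 cm between sides; suture difference 0.1 cm.

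- As printed, in mm, cm or inches: t = 1.71, p = 0.092, d = 1.71/√63 = 0.22.
- Divided by baseline: t = 1.72, p = 0.090, d = 1.72/√63 = 0.22.

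**5. Effect on the sample size.** None. The Protocol supports its effect size by saying that "moderate to large effect sizes can be expected for our key outcome, closure time". Swelling does not enter the calculation, so 63 and the recruitment target of 70 stand.

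**The case against.** The strongest reply is that this is a dropped fragment with an obvious meaning. The bracket stops just where a closing bracket and a divisor would stand, the outcome is labelled a percentage, and it is built from a before-and-after pair. Loss in reading the PDF is also possible. The division by 3 earlier in the sentence survived, which makes such a loss less likely but does not exclude it. The individual triplicate measurements are entered in the spreadsheet, and Data entry provides for an error check before analysis. A true percentage can therefore be computed at any time, and a reported swelling of 600% would probably be noticed.

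Most of this stands. It makes a slip the likely cause and means that no data are lost. It does not make the printed rule correct. The Protocol nowhere confirms the intended reading, and the study it cites for the formula could not be consulted. A value such as 60 or 20 is also less conspicuous than 600.

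Three stronger readings are tempting and are not supported:

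- A reader might infer that the trial's effect sizes are wrong by one or two orders of magnitude. The Protocol expresses effect size as Cohen's d, which a constant multiplier leaves unchanged; only the raw difference and its interval carry the wrong scale.
- A reader might infer that the power calculation is compromised. It rests on closure time.
- A reader might infer that the analysis model needs the baseline measurement as a covariate. That is a separate modelling preference and does not repair the formula.

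**Conclusion.** The point holds as a defect in the stated definition. As printed, the swelling outcome is 100 times a length difference. Over the assumed baselines of 110 to 130 mm, it exceeds relative swelling by a factor of 11 to 13 if the tape is read in centimetres and 110 to 130 if in millimetres. The consequence is confined to the raw mean difference, its confidence interval, the percent label and comparability with other studies.

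The within-patient test and the standardised effect are essentially unchanged, provided that one unit is used throughout; mixing units between patients would remove that protection. The sample size of 63 is untouched.

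The conclusion that the formula is wrong does not depend on the assumed face lengths; only the size of the distortion does. It does depend on the source page printing the same expression, which should be confirmed.

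**What to change.** First check the source page for a divisor lost in reading. If it is absent there too, restate the outcome in Measurement of facial swelling as:

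swelling (%) = [(post − pre) / pre] × 100,

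where post and pre are the means of A, B and C for the same side. Compute it for each side at each postoperative visit from that side's own preoperative value. State the tape unit once in that section and print it on the forms in Appendices 1 to 3.

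The cost is one line of Protocol wording, a unit label on the forms and one spreadsheet formula. Both sides are already measured before and after surgery, so no new data are needed, and the analysis model and the sample size stay as they are.
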